4 SELECTION AND ENROLLMENT OF PARTICIPANTS

Study Population: English-speaking (as discerned from the EMR) PLWD-Care partner dyads from the 4 participating clinics will be recruited. Dyads in the participating clinics will be identified in the following way:

- via warm handoff from a clinic provider to the ODC via the current standard of care for working with caregivers of PLWD regarding behavioral concerns, ODCs will be notified of the potential study participant by either of the two methods of ascertainment by the study RA. The ODC will then contact the care partner who is identified in the EMR as the responsible person or family member for the PLWD by telephone participation in the DICE program. We will also track the proportion of PLWD without a caregiver listed for study tracking.

Setting: Participants will be recruited from four primary care clinics in the Primary Care Network (total of 13) at University of California Davis. Clinics have been selected for the number of PLWD seen annually in each clinic. Below is preliminary information obtained on the potential subject population for the four study clinics from FY 1/1/2021-12/31/2021:

	Midtown	Elk Grove	ACC	FCC
>65 years old Dementia	63	67	66	76
Race/ethnicity				
White	40 (63.55)	35 (52.2%)	40 (63.5%)	27 (35.5%)
Black	11 (17.5%)	14 (20.9%)	11 (17.5%)	11 (14.5%)
Asian	8 (12.7%)	10 (14.9%)	8 (12.7%)	25 (32.9%)
Other	4 (6.4%)	8 (11.9%)	4 (6.3%)	
				13 (17.1%)

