9.1 Sample Size and Randomization

We will examine data across 4 clinics in order to assess the feasibility of a multi-site study. We selected 25 dyads per clinic as our sample size (primary study sample- total n=100 PLWD), and their caregiver (n=100) in order to have the ability to examine feasibility measures within clinic as well as across clinic with some accuracy. For example, the degree of accuracy around an enrollment rate of 75% overall is 18% (width of the 95% confidence interval), allowing us a tighter margin of error overall. Within clinic, accuracy is larger (width of 95% confidence interval 36%), suggesting more uncertainty, but allowing us to examine clinic-specific enrollment to ensure that there is consistency across clinics.

To determine the feasibility of ascertaining and analyzing the primary (psychotropic medication use) and secondary clinical outcomes (hospitalizations, ED visits and nursing home placement of PLWDs) from the existing health system-wide electronic medical record (EMR) participants (the primary study sample of PLWD n=100) will be measured after the 6-month DICE implementation period using the EMR and compared to corresponding outcomes for the four participating clinics in the 6 months prior to the intervention (historical controls n=100); all PLWD in the four participating clinics), (N=300).

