9.5 Data Analyses

Data will be summarized with descriptive statistics to allow us to review the demographics and clinical characteristics of our enrolled participants, as well as to review implausible values. The extent of missing data will also be assessed as a key indicator of feasibility of collecting data from clinic notes and the EMR; additionally, we will ascertain whether baseline characteristics are associated with missingness in order to modify study procedures for the larger trial. Feasibility will be characterized by rate of enrollment (# enrolled/# invited to enroll), number of contacts between ODCs and dyads (summarized as averages/SDs across dyads), and time requirements (summarized as averages/SDs). We will examine these overall and by clinic, to ensure consistency across clinics. We will summarize data on medication use (binary: psychotropic use or not) for the four clinics overall prior to the study and for enrolled PLWD post-intervention and will compare them using mixed models with a logit link to analyze these pre-post data, accounting for correlation within clinic. Models will first be fitted in a crude fashion, secondarily we will include covariate adjustment as a means to inform design characteristics in the ePCT, recognizing we have limited power to make definitive conclusions from these analyses. We will similarly examine healthcare utilization (counts of hospitalizations and ED visits; binary measure of nursing home placement) once we ensure that these data are feasibly collected from the EPIC EHR.

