Models will first be fitted in a crude fashion, secondarily we will include covariate adjustment to inform design characteristics in the ePCT, recognizing we have limited power to make definitive conclusions from these analyses. We will similarly examine healthcare utilization (counts of hospitalizations and ED visits; binary measure of nursing home placement) once we ensure that these data are feasibly collected from the EPIC EHR. In order to go on to the ePCT, we must meet two criteria. First, the primary feasibility outcome (enrollment rates) must be greater than 75%. Second, we must be able to show that the lower limit of the 90% confidence interval for testing the pre-post medication use is greater than a 25% decrease in the pre-study proportion. The former criteria is based on the observed enrollment rate in the pilot from the WeCareAdvisor study (17) of PLWD-care partner dyads; the latter is based on what is reasonable to assume will change in the shorter 6-month pilot and is clinically relevant.

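### Go criterion 1 is a ratio of enrolled to invited with no minimum count, so a pilot that recruits a small fraction of its 100 dyads can still meet it

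*Combined protocol and SAP*

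**What the plan says.** Section 9.5 defines the first feasibility measure as the "rate of enrollment (# enrolled/# invited to enroll"). It then sets the progression rule: "In order to go on to the ePCT, we must meet two criteria". Criterion 1 reads "First, the primary feasibility outcome (enrollment rates) must be greater than 75" percent. Criterion 2 concerns medication use and begins "Second, we must be able to show that the lower limit of the 90% confidence interval"; it sets that limit against a 25% decrease from the pre-study proportion.

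The recruitment target stands elsewhere. Section 9.1 says "We selected 25 dyads per clinic as our sample size (primary study sample- total n=100 PLWD") and justifies the number by precision: "the degree of accuracy around an enrollment rate of 75% overall is 18% (width of the 95% confidence interval"), and 36% within a clinic. Sections 1.1, 3 and 9.0 repeat the 100 and the 25 per site. No section makes 100, 25 per clinic, or any accrual rate a condition for going on.

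The table in Section 4, row ">65 years old Dementia", lists 63, 67, 66 and 76 people with dementia at the four clinics for calendar year 2021. Section 5.1 places the six-month study period in months 4 to 9.

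**The concern.** Section 1.1 makes feasibility the primary objective, in order to guide a full-scale trial. One main feasibility question is whether clinics can supply enough dyads. A ratio with invitations as its denominator cannot answer it. A clinic whose providers rarely hand patients over to the coordinator can still score above 75%, because the people never approached do not enter the calculation. Under the consent waiver, Section 6.2.1 makes DICE part of the coordinator's contact itself, which may push the ratio up further.

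The rule also compares a point estimate with 75%, with no confidence bound. The precision that justified 25 dyads per clinic is therefore not protected: the rule applies in the same way to 15 invitations as to 133. At stake is a pilot that reports its recruitment criterion as met when it has largely failed to recruit.

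**Working it through.** **Inputs.** Threshold above 75% and rate = enrolled/invited (Section 9.5). Target 4 × 25 = 100 and stated interval widths of 18% and 36% (Section 9.1). Annual counts 63 + 67 + 66 + 76 = 272 (Section 4).

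**1. The plan's own precision figures.** The exact (Clopper-Pearson) 95% interval for 75/100 is 65.3% to 83.1%, width 17.8 points. For 19/25 it is 54.9% to 90.6%, width 35.8 points. These round to the stated 18 and 36, so both figures are reproduced. They use the enrolled target as the denominator, whereas the rate's denominator is the number invited.

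**2. Criterion 1 at small numbers.** The smallest passing count is the smallest x with x/n > 0.75.
- 15 invited: x = 12 (80%), exact 95% interval 52% to 96%, width 44 points.
- 20 invited: x = 16 (80%), interval 56% to 94%, width 38 points.
- 50 invited: x = 38 (76%), interval 62% to 87%, width 25 points.

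The first two pass with 12% and 16% of the planned 100 dyads.

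**3. Chance of passing when the true rate is below the threshold.** With X binomial (n, 0.70), P(X ≥ 16) = 24% at n = 20 and P(X ≥ 76) = 11% at n = 100. The 70% is an assumed value. Recruiting few dyads roughly doubles the chance of a false pass.

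**4. Whether criterion 2 fills the gap.** Assumptions: 50% pre-study use, 100 controls, a 90% interval on the log risk ratio, and no allowance for clustering. With proportion p1 = x/n after and p0 before, SE = √[(1 − p1)/x + (1 − p0)/(100·p0)], and the limits are (p1/p0)·exp(±1.645·SE).
- Stricter reading (the whole interval lies beyond a 25% decrease, so the upper limit is below 0.75). The observed relative decrease needed is 46% with 100 enrolled (27 users), 52% with 50 (12 users) and 70% with 20 (3 users). With 12 enrolled, even one user gives an upper limit of 0.81, so it fails unless there are no users at all.
- Looser reading (the limit showing the larger decrease lies beyond 25%). Suppose use is 50% in both periods, so there is no effect. With 12 enrolled, SE = √(1/12 + 0.01) = 0.306 and the limit is exp(−1.645 × 0.306) = 0.605, a 39% decrease, which passes. With 100 enrolled, SE = 0.141 and the limit is 0.79, a 21% decrease, which fails.

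Small numbers therefore make criterion 2 harder on one reading and easier on the other.

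**5. What the target asks of the clinics.** 100/0.75 = 133.3 invitations, or 33.3 per clinic. 133.3/272 = 49%. By clinic, 33.3/63 = 53%, 33.3/67 = 50%, 33.3/66 = 51% and 33.3/76 = 44%. Over six months the benchmark is 33.3/6 = 5.6 invitations and 25/6 = 4.2 enrollments per clinic per month.

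Expected enrollment is 272 × (share seen in six months) × (share eligible and handed off) × 0.75. The documents give neither share. With half seen and half handed off it is 51; with three quarters seen and 0.7 handed off, 107; with all seen and 0.7 handed off, 143.

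**The case against.** The strongest objection is that 'go' needs both criteria. A reader might infer from 12 of 15 that a failed recruitment leads straight to the full trial. The documents do not support that: on the stricter reading of criterion 2, 12 enrolled dyads practically cannot satisfy it. This stands, and it limits the point to criterion 1. It does not remove the point, because criterion 2 measures medication use rather than recruitment, and the looser reading of its wording works the other way.

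A reader might also infer that the plan's own table shows 25 per clinic to be out of reach. Halving the annual count gives 133.3/136 = 98%, but that assumes no patient is seen in both halves of the year, which no section supports. Other text also points to a larger pool. The table covers only those over 65, while Section 4.1 sets no age limit for the person with dementia. Sections 3 and 9.0 mention electronic identification, although Sections 4 and 4.3 describe provider handoff. Section 5.1 provides for dyads without current behavioral symptoms. The objection stands: the documents leave attainability open.

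A shortfall would also be visible. Section 9.5 reports enrollment overall and by clinic, and Section 7.6 has the Safety Officer evaluate enrollment rates. That is true, but neither bears on the go rule.

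Lastly, 25 per clinic was chosen for precision, not as a progression threshold, and as a hard gate 24 in one clinic would fail the whole pilot. This too stands and shapes the fix.

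**Conclusion.** The concern holds for criterion 1. The criterion has no minimum count and can be met with 12 or 16 of the planned 100 dyads, at interval widths of 44 or 38 points rather than 18. At an assumed true rate of 70%, the chance of passing is 24% with 20 invited against 11% with 100. These results follow from the definition and the threshold and need no assumption about the clinics' supply of patients.

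That criterion 2 is an unreliable safeguard rests on its ambiguous wording; the figures shown assume 50% pre-study use and 100 controls. Attainability of the target is uncertain: about 49% of the listed annual population must be invited (44% to 53% by clinic), and the share reachable in six months is not given.

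A separate discrepancy does not affect this conclusion. The ACC race counts in Section 4 (40, 11, 8, 4) repeat Midtown's and sum to 63, not the 66 shown. Using 63 changes the overall need only from 49.0% to 133.3/269 = 49.6%.

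**What to change.** In Section 9.5, reword criterion 1 to require both the ratio above 75% and a total of 100 dyads enrolled by the end of month 9. Alternatively, fix a lower total before enrollment starts and justify it by the stated precision. For example, 76 enrolled of 100 invited has an exact 95% interval of 66% to 84%, about the 18 points that Section 9.1 cites.

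Report invitations and enrollments by clinic and month beside the benchmark of 25 per clinic (5.6 invitations and 4.2 enrollments per month). Keep that benchmark descriptive, not a hard gate for each clinic.

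Separately, re-check the ACC column in Section 4 and restate the table.

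The cost is protocol wording, tabulation of invitation and enrollment dates, and one repeated EMR count. The downside is that 'go' becomes somewhat harder to reach.

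### Go/no-go criterion 2 is mandatory but does not define its contrast, direction or control set, so the same data can give opposite verdicts

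*Combined protocol and SAP*

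**What the plan says.** Section 9.5 states: "In order to go on to the ePCT, we must meet two criteria". The first is an enrolment rate above 75%. The second is that "the lower limit of the 90% confidence interval for testing the pre-post medication use is greater than a 25% decrease in the pre-study proportion". On where the 25% comes from, the section says "the latter is based on what is reasonable to assume will change in the shorter 6-month pilot and is clinically relevant".

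The comparison is of binary psychotropic use, in the four clinics before the study against enrolled patients afterwards. For this the plan "will compare them using mixed models with a logit link to analyze these pre-post data, accounting for correlation within clinic". Where it describes the crude and adjusted models, it adds "recognizing we have limited power to make definitive conclusions from these analyses".

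Section 9.1 justifies the sample size through enrolment precision only: "the degree of accuracy around an enrollment rate of 75% overall is 18% (width of the 95% confidence interval". The same section describes the comparison group as "historical controls n=100); all PLWD in the four participating clinics". Elsewhere, Section 3 gives 100 controls, while Section 1 (secondary objectives) and Aim 2 in Section 9.0 give every person with dementia in the four clinics.

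No section states the pre-study proportion, the effect measure to which the 90% interval belongs, or the probability of meeting criterion 2.

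**The concern.** A mandatory decision rule should return one verdict for any given data set. This one leaves three things open.

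- **Contrast.** The model's direct output is an odds ratio, the threshold is a decrease in a proportion, and no conversion is given.
- **Direction.** A lower limit greater than a decrease means one thing if a decrease is coded positive and the opposite if the change is signed or expressed as a post/pre ratio.
- **Control set.** One hundred people and all people with dementia in four clinics are different samples. The plan does not say whether someone may be in both periods.

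The choice of reading could therefore be made after the data are seen, and it decides whether the full-scale trial goes ahead.

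**Working it through.** **The plan's own figure.** The stated 95% interval widths for a 75% enrolment rate reproduce with the exact binomial interval: 17.8% at n = 100 (stated 18%) and 36.2% at n = 25 (stated 36%). This supports the enrolment arithmetic but says nothing about criterion 2.

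**Inputs.** From the documents: 100 enrolled patients, 100 controls, a 90% interval (z = 1.645), and a 25% margin taken as relative (ratio 0.75). Assumed: pre-study use p0 of 30, 40, 50, 60 or 70%; independent groups; no clinic effect.

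**Four readings of the rule**, with R = post/pre ratio of proportions:

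1. Whole interval beyond a 25% decrease: upper limit of R < 0.75.
2. Interval need only reach a 25% decrease: lower limit of R < 0.75.
3. Words applied literally to a ratio: lower limit of R > 0.75.
4. Same margin on the model's direct output: upper limit of the odds ratio < 0.75.

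**Formulas**, with x0 and x1 users out of n0 and n1:

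- Limits of R: R·exp(±1.645·SE), SE² = 1/x1 − 1/n1 + 1/x0 − 1/n0.
- Limits of the odds ratio: OR·exp(±1.645·SE), SE² = 1/x1 + 1/(n1−x1) + 1/x0 + 1/(n0−x0).

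**Two illustrative data sets.**

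- 40/100 before, 30/100 after. R = 0.75; SE = √(0.0333 − 0.01 + 0.025 − 0.01) = 0.196; limits 0.54 to 1.03. OR = 0.64, SE = 0.299, upper limit 1.05. Reading 2 says go; readings 1, 3 and 4 say stop.
- 60/100 before, 60/100 after. R = 1; SE = √(2 × (1/60 − 1/100)) = 0.115; limits 0.83 to 1.21. OR = 1, so its upper limit is above 0.75. Reading 3 says go; readings 1, 2 and 4 say stop.

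Readings 2 and 3 thus reverse each other on both data sets.

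**Pass probability (%)**, by exact enumeration of two binomials, for p0 = 30/40/50/60/70%:

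| Reading | True 25% relative decrease | No effect |
|---|---|---|
| 1 | 4.6 / 4.5 / 4.5 / 4.6 / 4.4 | 0.1 or less |
| 2 | 94.9 / 94.9 / 94.9 / 94.8 / 94.5 | 62 / 49 / 35 / 20 / 8 |
| 3 | 5.1 / 5.1 / 5.1 / 5.2 / 5.5 | 38 / 51 / 65 / 80 / 92 |
| 4 | 9.1 / 12.8 / 19.6 / 30.9 / 46.5 | 0.4–0.5 |

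**Why reading 1 gives about 5%.** A 90% interval leaves 5% in each tail, so its limit clears the true value about 5% of the time. Enumeration at 50, 100, 200, 400 and 800 per group gives 4.2–4.9%, so a larger sample does not change it. For an 80% chance of passing under reading 1 with 100 per group, the true decrease must be about 65/59/55/51/47%.

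**Sensitivity of reading 1.** Section 4 says "Below is preliminary information obtained on the potential subject population for the four study clinics". Its counts sum to 63 + 67 + 66 + 76 = 272, which is only a proxy for all people with dementia: they are patients over 65 in calendar 2021, not the six-month control window. With 272 controls, reading 1 gives 3.9–4.1% at a true 25% decrease. A clinic-stratified simulation (25 per clinic per period, between-clinic SD on the logit scale 0 to 0.6) gives 4.7–5.0%.

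**The case against.** The strongest defence is that the intent is recoverable. A decrease in the pre-study proportion leans relative. A statistician would probably take the rule to mean that the interval must lie beyond 25%. If 25% is the smallest worthwhile change, a low pass rate at exactly 25% is what such a rule is meant to give. The study is also a pilot that admits limited power, and the baselines above are assumed.

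Much of this stands. Scale is the weakest of the gaps, and the percentage-point reading can be set aside. Reading 3 is implausible as intent; it matters only because it follows from the literal words once the contrast is a ratio. The figures other than the 5% for reading 1 depend on the baseline, and overlap between the groups would change the variance.

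A reader might go further and infer that the pilot is almost certain to stop, with a pass probability of 4–5%. The documents do not support that as the headline. It belongs to one reading and holds by construction. It is a power defect only if 25% is the expected effect, and 9.5 gives both bases for the number: a change reasonable to assume, and clinical relevance.

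The defence does not supply the missing definitions. The admission of limited power is attached to the models, yet the same comparison is then made a condition of proceeding.

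**Conclusion.** The point holds as a defect of definition in a mandatory rule. Depending on the reading, the chance of passing at a true 25% relative decrease runs from about 4% to about 95%. None of the three ratio readings both passes reliably at that decrease and stops reliably when nothing has changed: the first stops in both cases, the second can pass often with no effect, and the third passes more often with no effect than with a 25% decrease. The odds-ratio reading stops reliably under no effect but passes in fewer than half of cases at a 25% decrease.

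These sizes rest on 100 independent patients per period and assumed pre-study use of 30–70%. The ambiguity itself rests on the text alone. It should be corrected before post-intervention data are seen, because the rule decides whether the full-scale trial proceeds.

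**What to change.** 1. In 9.5, restate criterion 2 as a 90% interval for the post/pre ratio of model-standardised proportions from the planned logit mixed model. State which limit is compared with what, in which direction, and that 25% is relative.
2. In 9.1, name one control set and say whether a person may be in both groups.
3. Give the pass probability at no effect and at the expected decrease, using the pre-study proportion from the control extract.
4. State what 25% is. If it is the expected effect, do not require the 90% limit to clear that same value. If it is a minimum relevant change, state the larger expected decrease separately, with its pass probability; the 47–65% above shows what the whole-interval rule would need.

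The cost is a rewritten criterion in 9.5 and one statement in 9.1, agreed by the sponsor. No patients or data are added.

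Replacing the margin by an upper limit of the ratio below 1 is a sponsor option, not part of the repair, because it gives up the 25% threshold. With 100 per group it passes about 5% of the time under no effect and 32/42/56/69/81% at a true 25% decrease. It passes less often if participants, who enter by warm handoff for behavioural concerns, start with higher use than controls, who need only a dementia diagnosis. If their starting use were 20% higher in relative terms (an assumption), the expected ratio would be 1.2 × 0.75 = 0.90 and the pass probability about 12–27%.

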10 DATA COLLECTION AND QUALITY ASSURANCE

10.2 Data Collection Forms

Data will be collected from the electronic medical record. ODCs will put information about the use of the DICE Approach into their routine clinical notes. Exit interviews will be collected on paper and uploaded into secure study files.

10.3 Data Management

The UCD study team will be responsible for data collection. Data from the clinical notes as well as outcomes will be downloaded onto a secure server. A waiver of authorization for PHI data will be completed by the study team. The Drexel CO-I will be responsible for data management and analysis of a deidentified data set that is transferred from UCD and securely stored at Drexel.

10.4 Quality Assurance

10.3.1 Training

The study will take place in usual clinic care. The only added training will be the training in the DICE approach as described above. PIs and study personnel will be trained in Good Clinical Practice and HIPAA for research purposes.

10.3.2 Quality Control Committee

Not applicable

10.3.3 Metrics

Not applicable

10.3.4 Protocol Deviations

Will be submitted as applicable.

